# 1. **PROTOCOL SUMMARY**

### 1.1. Synopsis

**Protocol Title:** A Phase 1, Randomized, 2-Period, 2-Sequence, Cross-over Study to Determine the Effect of ALXN1840 on the Metabolism of a CYP2C9 Substrate in Healthy Participants.

**Short Title:** Phase 1 Study of ALXN1840 on the Metabolism of a CYP2C9 Substrate in Healthy Participants.

### **Rationale:**

ALXN1840 is considered to have potential for moderate drug-drug interactions (DDI) due to inhibition of cytochrome P450 2C9 (CYP2C9) according to in vitro studies using human liver microsomes and simulations performed to assess the potential for DDI risks. This study has been designed to determine the effect of ALXN1840 enteric-coated (EC) tablets at a single dose of 60 mg ( $4 \times 15$  mg) on the metabolism of celecoxib, a sensitive CYP2C9 substrate, at a single dose of 200 mg. A single dose of 60 mg ALXN1840 as a perpetrator is considered appropriate due to lack of potential for time-dependent inhibition (TDI) under the maximum observed ALXN1840 concentration in plasma after repeated daily dosing at steady state. A single dose of 200 mg celecoxib as a victim is considered appropriate due to the linear pharmacokinetics (PK) of celecoxib within the approved therapeutic dose range.

The 60 mg dose of ALXN1840 is the maximum allowed daily dose in the on-going Phase 3 Study WTX101-301 in patients with Wilson disease (WD). The 200 mg celecoxib single dose has been selected based on the drug interaction study with fluconazole as described in the Celebrex® United States Prescribing Information (USPI) (Celebrex®) and Diflucan® USPI (Diflucan®).

#### **Objectives and Endpoints**

Objectives	Endpoints
Primary	
• To determine the effect of ALXN1840 on the PK of celecoxib, a sensitive CYP2C9 substrate	
 
PK parameters of celecoxib (maximum observed plasma concentration [Cmax], area under the plasma concentration (AUC) versus time curve from time 0 to the last quantifiable concentration [AUCt], and AUC versus time curve from time 0 to infinity [AUC∞]) with and without the coadministration of ALXN1840
 

Secondary	

 
To determine the effect of ALXN1840 on the PK of plasma molybdenum (Mo) with the coadministration of celecoxib
 
To determine the safety and tolerability of ALXN1840, with the coadministration of celecoxib
 
	
 
PK parameters for plasma total Mo (Cmax, AUCt, and AUC∞) with the coadministration of celecoxib
 
Safety assessed by incidence of treatment-emergent adverse events (TEAEs) and treatment-emergent serious adverse events (TESAEs), physical examination, vital signs measurements, clinical laboratory and 12-lead electrocardiogram (ECG) results
 

Abbreviations:  $AUC_{\infty}$  = area under the plasma concentration versus time curve from time 0 to infinity;  $AUC_t$  = area under the plasma concentration versus time curve from time 0 to the last quantifiable concentration;  $C_{max}$  = maximum observed plasma concentration of the drug; CYP2C9 = Cytochrome P450 2C9; ECG = electrocardiogram; Mo = molybdenum; PK = pharmacokinetics; TEAE = treatment-emergent adverse event; TESAE = treatment-emergent serious adverse event.

#### **Overall Design**

This is a Phase 1, randomized, 2-period, 2-sequence, cross-over study designed to determine the effect of ALXN1840 on the metabolism of celecoxib, a sensitive CYP2C9 substrate, in healthy male and female participants. The safety and tolerability of ALXN1840 will be determined along with ALXN1840 PK in plasma as measured via total Mo with the coadministration of celecoxib.

**Disclosure Statement**: This is an open-label, 2-period, 2-sequence, cross-over study in healthy participants with randomization to 2 treatment sequences.

#### Number of Participants:

It is planned that approximately 38 participants will be enrolled at a single site.

#### **Intervention Groups and Duration:**

The study has a Screening Period (Day -28 to Day -2), two 11-day study periods (Day 1 to Day 11) with a minimum of 14 days between doses of celecoxib, and an End of Study (EOS) Visit (Day  $15 \pm 2$  days) after Period 2 dosing. Participants will report to the clinical research unit (CRU) on the day prior (Day -1) to both dosing periods.

In each study period, participants will receive one of the 2 treatments noted below:

- Treatment A: One 200 mg celecoxib capsule with 240 mL water (fasting).
- **Treatment B**: One 200 mg celecoxib capsule + 4 × 15 mg ALXN1840 EC tablets with 240 mL water (fasting).

Participants will receive each treatment as a single dose administration in the sequence as defined below.

Sequence	Treatmen	t sequence	Female a	Total	
number	Study Period 1	Study Period 2			
1	А	В	8 to 11	8 to 11	19
2	В	А	8 to 11	8 to 11	19
Total			16 to 22	16 to 22	38

a In an effort to achieve balance between males and females in each sequence, there will be no less than 16 and no more than 22 of either sex (ie, a maximum split in either direction of approximately 60%:40%). Randomization will be stratified by sex.

Treatment A – One 200 mg celecoxib capsule with 240 mL water (fasting)

Treatment B – One 200 mg celecoxib capsule +  $4 \times 15$  mg ALXN1840 enteric-coated tablets with 240 mL water (fasting)

The time between dosing celecoxib alone or in combination with ALXN1840 in each treatment sequence will be a minimum of 14 days. Based on the estimated mean ALXN1840 half-life of approximately 2 days in healthy participants (under oral dose of 60 mg), a 14-day period between doses of celecoxib is considered sufficient to eliminate, on average, approximately more than 99.2% of the plasma total Mo before the next dose of celecoxib is administered. The mean elimination half-life ( $\pm$ SD) of celecoxib after chronic dosing is 11.2 ( $\pm$  3.5) hours (Celebrex®), A 14-day period between doses of celecoxib is sufficient to eliminate, on average, more than 99.2% of the plasma celecoxib before the next dose of celecoxib is administered.

Participants will return to the CRU on Day 15 ( $\pm$  2 days) following Period 2 dosing for the EOS Visit with follow-up procedures, and to determine if any adverse events (AEs) have occurred since the last study visit. If participants withdraw from the study early, they will be seen and assessed by the Principal Investigator, and whenever possible, they are to undergo the procedures associated with the EOS Visit. Participants may be replaced at the discretion of Alexion.

[figure not shown]
Participants may be asked or required to stay in the CRU between Periods 1 and 2, and/or before the EOS visit, for their own safety, and also to maintain the integrity of the conduct of the study.

### **Data Monitoring Committee:**

There will not be a Data Monitoring Committee, but provision is included for an ad hoc Safety Review Committee, if needed.

### 1.2. Schema

Participants will be admitted on Day -1 of each period for Check in procedures. Eligible participants will be randomized on Day 1 immediately prior to dosing in Period 1.

Participants will receive treatment (A or B) based on randomization on Day 1 of each period.

Blood samples for PK analysis of total Mo (as a measure of ALXN1840) and celecoxib will be collected in each period on Day 1 at pre-dose, 1, 2, 3, 4, 5, 6, 8, 12 and 24 hours (Day 2) and then at 24 hour intervals on Days 3, 4, 5, 6, 7, 8, 9, 10, and Day 11. The nominal 336-hour sample for Period 1 will be collected pre-dose in Period 2. Participants will be discharged on Day 11 of each period after completion of all procedures and review of all safety data. The end of study visit (EOS) will occur on Day  $15 \pm 2$  of Period 2, with the collection of 336-hour PK sample for Period 2.

Participants may be asked or required to stay in the CRU between Periods 1 and 2, and/or before the EOS visit, for their own safety, and also to maintain the integrity of the conduct of the study.

# **1.3.** Schedule of Activities

### Table 1:Schedule of Activities

Study Procedures	S a	C-I b		Treatment Periods 1 and 2									EOS or ET c										
$Days \rightarrow$	-28 to -2	-1						1					2	3	4	5	6	7	8	9	10	11	15 (±2)
$Hours \rightarrow$			Pre- dose	0 d	1	2	3	4	5	6	8	12	24	48	72	96	120	144	168	192	216	240	336 e
Eligibility																							
Informed consent	х																						
Inclusion/exclusion criteria	х	х																					
Pregnancy test	Х	Х																					х
Urine alcohol test	Х	Х																					
Urine drug screen	Х	Х																					
HIV, hepatitis B and C screen	х																						
Study Administrative																				•			
Medical history/demographics f	x																						
Physical examination g	Х	Х																					х
Weight	Х	Х																					
Height and BMI	Х																						
Discussion/documentation of contraception method	x	x																					
Randomization				x h																			
Administration of Study I	nterve	ention	i																				
Treatment A: celecoxib or Treatment B: celecoxib + ALXN1840				x																			
PK Blood Sample																					•		•
Celecoxib and ALXN1840 PK			x		x	x	x	x	x	x	x	x	x	x	x	x	x	х	x	x	x	x	х
Pharmacogenetic sample																							
CYP2C9 genotyping		Х																					

Study Procedures	S a	C-I b		Treatment Periods 1 and 2								EOS or ET c											
$Days \rightarrow$	-28 to -2	-1						1					2	3	4	5	6	7	8	9	10	11	15 (±2)
Hours $\rightarrow$			Pre- dose	0.	1	2	3	4	5	6	8	12	24	48	72	96	120	144	168	192	216	240	336 e
Laboratory Assessments																				•			•
Chemistry j , hematology, coagulation	x	x											x			x					x		x
Follicle stimulating hormone k	x																						
Urinalysis	Х	Х																					
Vitals signs measurements	Х		х		х			х			х	х	х										х
12-Lead ECG 	х		х					х															
Retained sample (safety) m			х																				
AE monitoring and concomitant therapies review	•				·															•		.	·

#### Table 1: Schedule of Activities (Continued)

a Within 28 days prior to Day 1 of the first dose of study drug in Dosing Period 1. Note that Screening only occurs once.

b Participants will be admitted to the CRU at least 10 hours prior to study intervention.

c Participants are required to return to the CRU approximately Day 15 ( $\pm 2$  days) following the final dose of study medication for an EOS evaluation.

Participants may be asked or required to stay in the CRU between Periods 1 and 2, and/or before the EOS visit, for their own safety, and also to maintain the integrity of the conduct of the study. In the event of early termination/discontinuation (ET), the procedures listed at the EOS are performed prior to participant discharge.

d Hour 0 corresponds to the time of celecoxib  $\pm$  ALXN1840 administration. Unless stated otherwise, times listed are in relation to celecoxib  $\pm$  ALXN1840 dosing.

e The nominal 336-hour sample for Period 1 to be collected pre dose in Period 2.

f Parameters include age and sex. Race and ethnicity will be collected where permitted by local regulations.

g A full physical examination will be performed at Screening, Check-in for each period, and at the end of the study or upon ET. A symptom-driven physical examination may be performed at other times, at the PI's discretion.

h Randomization will occur before dosing.

i Each dose administration will be separated by at least 14 days between celecoxib alone or in combination with ALXN1840 doses. There will be a minimum of 14 days between Day 1 of Period 1 and Day 1 of Period 2.

j Samples for chemistry will be obtained following a fast of at least 6 hours at Screening, and at Check-in. In case of dropouts, rechecks, and post dose chemistry, fasting is not required (Section 10.2).

k Only needed if claiming exemption from contraception requirement due to menopause.

 Triplicate 12-lead ECG will be taken at screening, pre-dose, and at 4 hours post-dose (before lunch) on Day 1. ECGs will be conducted before PK blood sampling if these 2 events are scheduled to occur at the same time.

m A single 15 mL sample will be retained for evaluation in the event of an unexpected safety finding; retained samples may be destroyed after completion of the clinical study report. The retained serum sample will only be collected pre-dose on Day 1 of Period 1.

Abbreviations: AE = adverse event; BMI = body mass index; C-I = Check-in; CRU = clinical research unit; ECG = electrocardiogram; EOS = End of Study; ET = Early Termination; FSH = follicle-stimulating hormone; HIV = human immunodeficiency virus; HR = heart rate; PI = Principal Investigator; PK = pharmacokinetics; S = Screening.

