3.3.2. Secondary Endpoints

The secondary endpoints include following PK parameters for plasma total Mo with the coadministration of celecoxib and safety assessed parameters

- The PK parameters
 - C_{max}
 - AUC_t
 - AUC_{∞}

- The safety parameters
 - Incidence of treatment-emergent adverse events (TEAEs) and treatmentemergent serious adverse events (TESAEs)
 - Physical examination (PE)
 - Vital signs measurements
 - Clinical laboratory results
 - 12-lead ECG results

4. General Statistical Considerations

All data captured on the case report form (CRF), laboratory safety variables, and PK assessments will be listed on an individual basis by treatment sequence and participant. Summary tables will be presented by treatment and overall, unless otherwise specified.

All pre- and post- dose assessments including repeated and/or unscheduled assessments will be included in the data listing.

Continuous variables will be described using the following descriptive statistics: number of non-missing values (n), arithmetic mean, standard deviation (SD), median, Q1, Q3, IQR, minimum, and maximum, unless otherwise specified. Categorical variables will be summarized using percentages and frequency count.

For the summary statistics of all continuous variables unless otherwise specified, minimum and maximum will be presented to the same number of decimal places as the raw data, mean, median, Q1, Q3, and IQR will be presented to one more decimal places than the raw data, and SD will be presented to two more decimal places than the raw data.

Percentages will be suppressed when the count is zero and will be presented to one decimal place. The denominator for all percentages will be the number of participants in the treatment sequence for the population of interest, unless otherwise specified.

Baseline is defined as the last non-missing assessment (including repeated and unscheduled assessments) prior to treatment on Day 1 (dose day for each period), unless otherwise specified. If there are repeated assessments at a time point, the first non-missing assessment will be included in the summary tables. If the original scheduled measurement at that time point is missing, the next available repeated measurement will be used in the summary tables.

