8.2. Clinical Laboratory Evaluations

Laboratory assessments (including chemistry, hematology, and coagulation) will be performed at Screening, Check-in for each period, Day 2 for each period, Day 5 for each period, Day 10 for each period, and EOS or ET.

Urinalysis will be performed at Screening and Check-in for each period.

Summary statistics and change from baseline for chemistry, hematology, and coagulation will be presented by treatment and by visit. Laboratory parameter values will be graded according to the National Cancer Institute CTCAE. Shift tables will be produced for chemistry, hematology, and coagulation. Shift from baseline grade relative to the reference ranges tables will be presented by treatment and by visit. Shift from changes to the worst highest grade assessed post-dose during the study tables will be presented by treatment. Last recheck values collected prior the dose of treatment will be used as baseline and all rechecks will be deleted from post-dose observations in calculating summary statistics.

All clinical laboratory tests (including chemistry, hematology, coagulation, and urinalysis) will be presented in data listings.

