8.2.1. Chemistry

Serum chemistry evaluation will include blood urea nitrogen, potassium, bicarbonate, sodium, glucose, aspartate aminotransferase, alanine aminotransferase, chloride, alkaline phosphatase, direct bilirubin, total bilirubin, albumin, creatinine, and creatine phosphokinase.

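### Chemistry is fasted before dosing but need not be afterwards, and the SAP ignores fasting status, so within-treatment glucose change and shift tables can carry a meal effect

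*Protocol*

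**What the plan says.** Footnote j to Table 1 of the protocol (Section 1.3) sets two conditions for one panel. Before dosing: "Samples for chemistry will be obtained following a fast of at least 6 hours at Screening, and at Check-in". Otherwise: "In case of dropouts, rechecks, and post dose chemistry, fasting is not required". The footnote refers to Section 10.2, which contains no fasting instruction.

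SAP Section 8.2 gives the laboratory schedule after Screening as "Check-in for each period, Day 2 for each period, Day 5 for each period, Day 10 for each period, and EOS or ET". SAP Section 8.2.1 puts glucose in the panel: "Serum chemistry evaluation will include blood urea nitrogen, potassium, bicarbonate, sodium, glucose". No lipids are listed.

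The general baseline rule (SAP Section 4) is "Baseline is defined as the last non-missing assessment (including repeated and unscheduled assessments) prior to treatment on Day 1", applied in each period. For laboratory data, SAP Section 8.2 adds "Last recheck values collected prior the dose of treatment will be used as baseline and all rechecks will be deleted from post-dose observations".

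On reporting, SAP Section 8.2 states "Summary statistics and change from baseline for chemistry, hematology, and coagulation will be presented by treatment and by visit". It also plans shift tables from baseline grade by visit, and to the worst post-dose grade by treatment. Fasting status does not appear as a variable, flag or restriction. Clinical laboratory results are among the secondary safety endpoints (SAP Section 3.3.2).

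**The concern.** A change from baseline can be read as a drug effect only if the two samples were taken under like conditions. Here the baseline is normally fasted, while the later sample may or may not be. Glucose responds to food, so a rise after dosing could reflect breakfast, and nothing planned for the dataset would separate the two explanations.

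The worst-grade shift table is the more exposed summary. A single unfasted draw can set a participant's entry if the rise crosses a grade boundary.

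The baseline has a smaller weakness of its own. A pre-dose recheck replaces the Check-in value, and footnote j exempts rechecks from the fast.

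At stake is how the within-treatment glucose tables are read. Glucose is the one clear example in this panel.

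**Working it through.** The plan states no figure on this point, so there is none to reproduce. The check traces the fasting rule through the baseline and reporting rules, then sizes the possible effect.

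**Inputs from the documents**
- Check-in chemistry: fast of at least 6 h. Post-dose chemistry and rechecks: no fast required (Table 1, footnote j).
- Post-dose chemistry: Days 2, 5 and 10 of each period, at 24, 96 and 216 h, plus EOS (Table 1; SAP 8.2).
- Dosing is in the morning (Protocol 6.1) and participants stay in the unit to Day 11 (Protocol 4.1). Since 24, 96 and 216 h are 1, 4 and 9 whole days after the dose, these draws fall in the morning.
- About 38 participants, 19 per sequence (Protocol Table 3).

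**Inputs assumed, because the documents do not give them**
- m, the mean rise in glucose in an unfasted sample: 5 to 20 mg/dL.
- p, the share of post-dose samples taken unfasted: 0.1 to 1.

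**Within-treatment change from baseline.** With a fasted baseline, the meal contribution to the mean change is p × m.

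| m (mg/dL) | p = 0.1 | p = 0.5 | p = 1 |
|---|---|---|---|
| 5 | 0.5 | 2.5 | 5 |
| 10 | 1 | 5 | 10 |
| 20 | 2 | 10 | 20 |

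If a share b of the baselines is also unfasted, the contribution becomes (p − b) × m. Unfasted baselines thus pull the other way and make the mixture harder to interpret.

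**Worst post-dose grade.** With three in-unit draws per period, treated as independent, the chance that at least one is unfasted is 1 − (1 − p)³. At p = 0.1 this is 1 − 0.729 = 27%. At p = 0.3 it is 1 − 0.343 = 66%. This is the chance of exposure to a meal effect, not of a changed grade.

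**Treatment B minus Treatment A.** The meal contribution is (p_B − p_A) × m. It is zero when the unfasted shares are equal. If they differ by 0.1, it is 0.1 × 5 = 0.5 to 0.1 × 20 = 2 mg/dL.

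**EOS.** This visit follows Period 2 only. Values under B therefore come from sequence AB and values under A from sequence BA: about 19 different participants on each side before dropout. The two treatments are not compared within the same person.

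**Number of samples.** Scheduled post-dose chemistry is 3 × 2 + 1 = 7 draws per participant, so at most 7 × 38 = 266. Of these, 6 × 38 = 228 are in-unit and 38 are at EOS. These are upper limits on scheduled samples, not counts of unfasted ones.

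**The case against.** The strongest reply is that waiving a fast does not mean participants have eaten. The in-unit draws are in the morning, and Protocol Section 8.2 places blood sampling ahead of a meal when the two coincide. Many of these samples may be fasted in practice. That is a fair limit on the size of p, but it does not close the gap. The ordering applies only to procedures scheduled together, and only as far as possible. Table 1 schedules no meals, and footnote j expressly lifts the requirement. EOS is normally a return visit without meal control, although participants may be kept in the unit before it.

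A second reply is that both treatments follow the same rule in the same people, so a shared meal shift cancels in B minus A. This stands for Days 2, 5 and 10, provided the unfasted shares are similar. It does not help the within-treatment tables, nor EOS, where only randomisation balances the groups on average.

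Third, an unfasted baseline should be rare. The Check-in evening meal must finish by 2100 and breakfast is omitted on Day 1 (Protocol Table 4), so a recheck on the dosing morning follows an overnight fast. A recheck drawn after the Day -1 meal is the narrow case left. Post-dose rechecks do not enter the summaries at all.

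Finally, laboratory safety is descriptive, with no inference planned (SAP Section 8), and glucose is not among the ALXN1840 risks in Protocol Table 2. That keeps the point minor. It also means the tables are read at face value, with no model to adjust them.

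**Conclusion.** The point holds as a minor, inexpensive improvement. The fasting rule differs before and after dosing, and the SAP neither records nor uses fasting status. Within-treatment glucose change and grade-shift summaries can therefore include a meal effect of p × m: 0.5 to 20 mg/dL over the assumed ranges. The size rests entirely on those assumptions.

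A reader might infer that every post-dose column contains the full fed-minus-fasted difference. The documents do not support that: it requires p = 1, and they permit unfasted samples without saying that samples are taken fed. A reader might also infer that the A versus B comparison is biased throughout, or that many analytes are affected. The crossover largely protects that comparison outside EOS, and only glucose is a clear case. The primary celecoxib pharmacokinetic analysis is unaffected.

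**What to change.** **Protocol, Table 1 footnote j.** Require the Day 2, 5 and 10 chemistry samples, and any pre-dose recheck that will serve as baseline, to be drawn before a meal under the same fast of at least 6 hours as Check-in. Record fasting status at every chemistry draw, including EOS. Either put the fasting rule into Section 10.2 or remove the pointer to it.

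**SAP Section 8.2.** Flag unfasted glucose values. Present glucose change and shift summaries for fasted samples alongside those for all samples. State that an unfasted recheck does not replace a fasted glucose baseline.

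The cost is breakfast timing on three in-unit mornings per period and one extra CRF field, with no additional draws. A compulsory fasted EOS visit is not needed, nor is discarding unfasted safety data: recording the status and showing both summaries is enough.
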